10.4 Target lesion assessment guidelines

The longest diameter (LD) for the target lesion (or lesions) will be calculated from the treatment planning CT scan using pulmonary and/or mediastinal windowing and reported as the baseline LD. The baseline LD will be used as a reference by which to characterize the objective tumor.

Local treatment effects in the vicinity of the tumor target may make determination of tumor dimensions difficult. For example, bronchial or bronchiolar damage may cause patchy consolidation around the tumor that over time may coalesce with the residual tumor. In cases in which it is indeterminate whether consolidation represents residual tumor or treatment effect, it should be assumed that abnormalities are residual tumor.

10.4 Criteria for Removal from Protocol Treatment

All reasons for discontinuation of treatment must be documented. All patients will be followed until death or 5 years post treatment (whichever time point comes first). If protocol treatment is discontinued for any reason other than death, follow up and data collection will continue as specified in the protocol.

10.4.1 Unacceptable toxicity.

10.4.2 A greater than two week delay in protocol treatment, as specified in Sections 6.0.

10.4.3 Development of intercurrent, non-cancer-related illnesses that prevent either continuation of therapy or regular follow-up.

10.5 Other response parameters

10.5.1 Time to Local Progression: The time to progression will be measured from the date of study entry to the date of documented local progression as determined by clinical exam.

10.5.2 Overall Survival: The survival time will be measured from the date of accession to the date of death. All patients will be followed for survival. Every effort should be made to document the cause of death.

10.5.3 Disease-Specific Survival : Disease-specific survival will be measured from the date of study entry to the date of death due to lung cancer. The following will be considered as failure events in assessing disease specific survival:

Death certified as due to lung cancer.

Death from other causes with active malignancy (clinical progression).

Death due to complications of treatment, irrespective of the status of malignancy.

Death from other causes with previously documented relapse but inactive at the time of death will not be considered in disease-specific survival, but will be analyzed separately.

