10.3 Response Assessment (RECIST Criteria)

Response will be evaluated in this study using the international criteria proposed by the Response Evaluation Criteria in Solid Tumors (RECIST) Committee [JNCI 92(3): 205-216, 2000]. See

<http://ctep.cancer.gov/protocolDevelopment/docs/therasserecistjnci.pdf> for further details.

Response Criteria: Evaluation of target lesions

*Complete Response (CR): Disappearance of all target lesions

*Partial Response (PR): At least a 30% decrease in the sum of the LD of target lesions, taking as reference the baseline sum LD

*Progressive Disease (PD): At least a 20% increase in the sum of the LD of target lesions, taking as reference the smallest sum LD recorded since the treatment started or the appearance of one or more new lesions

*Stable Disease (SD): Neither sufficient shrinkage to qualify for PR nor sufficient increase to qualify for PD, taking as reference the smallest sum LD since the treatment started

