11.0 Data Collection

Data should be submitted to:

**Department of Radiation Oncology
Clinical Research Office
The University of Texas Southwestern Medical Center
Attention: [name], Project Manager
[name]
[name]
[contact]**

Patients will be identified only by initials (first middle last) and a unique study ID number assigned to each study participant; if there is no middle initial, a hyphen will be used (first-last). Last names with apostrophes will be identified by the first letter of the last name. Participating sub-sites must remove or black-out identifiers from source documentation that is sent to UTSW.

Item	Due
Demographics	Within 2 weeks of study entry
Eligibility and Entry Characteristics, including baseline H&P and Zubrod PS	Within 2 weeks of study entry
Pathology Report	Within 2 weeks of study entry
Follow-up H&P data	At post XRT follow-up at 1, 3, 6, 9, and 12 months, then q 4 months year 2, after 2 years at the discretion of the investigator/institution
Tumor response evaluation	At post XRT follow-up at 3, 6, 9, and 12 months, then q 4 months year 2, after 2 years at the discretion of the investigator/institution
Adverse Event assessment	After each weekly treatment visit, then post XRT follow-up at 1, 3, 6, 9, and 12 months, then q 4 months year 2, after 2 years at the discretion of the investigator/institution

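### Local progression is dated by clinical exam and 12.2.1 names no event source, although CT-based tumor evaluation is already scheduled through year 2

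*Combined protocol and SAP*

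**What the plan says.** All references are to the combined protocol and SAP.

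- **10.5.1** has time to local progression "measured from the date of study entry to the date of documented local progression as determined by clinical exam". It does not mention regional failure or imaging.
- **10.3** adopts RECIST. Progressive disease is "At least a 20% increase in the sum of the LD of target lesions" relative to the smallest sum since treatment began, or "the appearance of one or more new lesions", with no limit on site.
- **10.4 (Target lesion assessment guidelines)** has the baseline longest diameter (LD) "calculated from the treatment planning CT scan". Where consolidation cannot be told from tumor, "it should be assumed that abnormalities are residual tumor".
- **11.0** makes tumor response evaluation due "At post XRT follow-up at 3, 6, 9, and 12 months", then every 4 months in year 2 and at discretion afterwards. **Appendix II** puts chest CT on the same visits. History and physical fall on those visits plus month 1.
- **2.2.1 and 12.1.4** make local-regional control a secondary endpoint. **12.2.1** estimates local-regional and distant failure by cumulative incidence. It defines neither event and refers to neither 10.3 nor 10.5.1.
- **10.5.2** defines survival thus: "The survival time will be measured from the date of accession to the date of death". The start point is worded differently from 10.5.1.

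**The concern.** Two analysts could both follow the protocol and report different local-regional failure rates, one from exam dates and one from CT. The only rule stated for a local progression date names the exam, while the serial measurements that 10.3 and 10.4 call for go unused for that purpose. It also stops at local progression, whereas the analysed event is local-regional.

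The direction of the risk depends on whether exam lags CT for disease inside the chest. If it does, some failures are dated late and others are never recorded because the patient dies first. Section 1.1 cites median survival of 9.5 and 10.3 months in a poor-risk population, so a delay of one visit is not trivial. Reported control would then be too favourable.

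**Working it through.** The plan states no figure for this endpoint, so there is nothing to reproduce. The check has two parts.

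**Schedules.** Chest CT and tumor evaluation after treatment fall at months 3, 6, 9, 12, 16, 20 and 24 (7 times). History and physical fall at the same 7 visits plus month 1. From month 3 on, every exam visit already has a CT, so dating by CT adds no visit.

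**Illustration of a lag.** The inputs are assumptions except where a source is given.
- Net 12-month failure F = 30%. Section 1.1 quotes local failure of 22-50% without a time point.
- Median survival 10 months, between the 9.5 and 10.3 in 1.1; death independent of failure.
- Visits are timed from the end of treatment but 10.5.1 counts from study entry, so each visit is shifted by s. Fifteen fractions at five per week give s = 0.7 months; adding the 4 weeks allowed by 6.1 gives s = 1.6.
- The lag from CT to exam is not given anywhere in the documents; 0 to 3 months is tried.

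Formulas: d = ln2/10 = 0.0693 per month; l = -ln(1-F)/12 = 0.0297 per month; v_k = nominal month + s, v_0 = 0.

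Recorded = sum over k of [exp(-l·v_(k-1)) - exp(-l·v_k)] · exp(-d·(v_k + lag)), keeping terms with v_k + lag ≤ 12.

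For s = 0.7 the visits are at 3.7, 6.7, 9.7 and 12.7 months:
- No lag: 8.06 + 4.80 + 3.57 = 16.4%. The 12.7-month visit is outside the window.
- Lag 3: 6.55 + 3.90 = 10.4%. The third term, 2.90, is dropped because 9.7 + 3 = 12.7 exceeds 12.

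| Lag (months) | s = 0.7 | s = 1.6 |
|---|---|---|
| 0 | 16.4% | 16.9% |
| 1 | 15.3% | 15.8% |
| 2 | 14.3% | 11.9% |
| 3 | 10.4% | 11.1% |

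**Splitting the 3-month drop (s = 0.7).** Keeping the dropped visit gives 10.45 + 2.90 = 13.3%. So of the 6.0 points, 16.4 - 13.3 = 3.1 are failures lost to death (1 - 0.5^(3/10) = 18.8% of 16.4) and 13.3 - 10.4 = 2.9 are cutoff at month 12. For s = 1.6 the same cutoff step comes between lags of 1 and 2 months.

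**24 months.** With visits through month 24 and every failure recorded one visit late, 23.1% becomes 17.2-17.3%.

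**No lag.** Exam with its extra month-1 visit records 17.0-17.8%, slightly above CT.

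**Opposite direction.** If CT over-calls at an assumed net 12-month rate c, adding hazard -ln(1-c)/12 gives 18.5-19.0% for c = 5% and 20.5-21.1% for c = 10%.

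**Sampling error.** 1.96·sqrt(0.164·0.836/n) is 10.8 points for n = 45 and 18.7 for n = 15.

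**The case against.** The strongest case against is that no direction of bias is established. Nothing in the documents says exam lags CT, and the two share every visit from month 3. Section 6.9.1 expects radiographic change in lung receiving 20 Gy or more, usually within six months of starting treatment, and the target lesion guidelines in 10.4 count indeterminate consolidation as tumor. CT dating could therefore over-call failure, and exam dating might be a defensible choice. This stands: it is why the proposed definition needs a sensitivity analysis and why no direction is claimed.

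Exam may also have been meant to include that visit's CT. That is possible, but 11.0 and Appendix II list history and physical separately from tumor evaluation, and nothing says one includes the other. Even on that reading, regional failure and the site of new lesions would remain undefined.

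Two stronger readings are tempting and not supported:
- A reader might infer that control is overstated by about 6 points. That needs a full 3-month lag for every failure, and about half of it is cutoff at month 12.
- A reader might infer that unmodified RECIST progression would be used, so that distant lesions count as local-regional. Section 12.2.1 estimates distant failure separately, which makes that unlikely.

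Parts of a fuller rewrite would also be redundant. The competing-risk reference cited in 12.2.1 implies death as the competing event. Follow-up is not stopped by distant failure: "All patients will be followed until death or 5 years post treatment". The accession wording in 10.5.2 is clerical.

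**Conclusion.** The point holds as a cheap improvement of minor severity. Section 10.5.1 states a rule that omits regional failure and does not use the CT evaluations already scheduled, and 12.2.1 does not say whether that rule or RECIST supplies the event. These are facts of the text and need no assumption.

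The size and direction of any bias are unknown. Under the assumptions above (s = 0.7), lags of 1, 2 and 3 months cost about 1.1, 2.1 and 6.0 points of recorded 12-month failure, and a zero lag costs none. CT over-call would act the other way. All of these shifts are smaller than the sampling half-width of 11 to 19 points, although a consistent lag would be systematic. The endpoint is descriptive, and the DLT definition, the MTD rule and the 7-45 patient range are unaffected.

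**What to change.** In 10.5.1, replace the clinical-exam clause with a single definition of local-regional failure, as the earlier of:

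(a) the first CT showing at least a 20% increase from nadir in the sum of LD of irradiated target lesions, or new disease in the treated region or regional nodes, with the study team stating the boundary; and

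(b) documented clinical local-regional failure when no CT is obtained.

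Class new lesions elsewhere as distant failure, and cite this definition in 12.2.1. Add a sensitivity analysis that excludes failures resting only on consolidation scored as tumor under the target lesion guidelines in 10.4. Using one term for the time origin in 10.5.1 and 10.5.2 would be a clerical tidy-up.

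Cost: the text change, one or two added items on the tumor evaluation form (lesion site, and whether the call rests on consolidation alone), and one extra analysis. No visit or scan is added through year 2. The drawbacks are possible CT over-call and a control estimate that may look less favourable. After year 2 imaging is discretionary, so ascertainment there remains uneven under any definition.

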10.6 Comorbidity Data and Rating

The Charlson Comorbidity index will be used to assess pretreatment comorbidity status per Appendix V.

11.0 Data Collection

Data should be submitted to:

**Department of Radiation Oncology
Clinical Research Office
The University of Texas Southwestern Medical Center
Attention: [name], Project Manager
[name]
[name]
[contact]**

Patients will be identified only by initials (first middle last) and a unique study ID number assigned to each study participant; if there is no middle initial, a hyphen will be used (first-last). Last names with apostrophes will be identified by the first letter of the last name. Participating sub-sites must remove or black-out identifiers from source documentation that is sent to UTSW.

Item	Due
Demographics	Within 2 weeks of study entry
Eligibility and Entry Characteristics, including baseline H&P and Zubrod PS	Within 2 weeks of study entry
Pathology Report	Within 2 weeks of study entry
Follow-up H&P data	At post XRT follow-up at 1, 3, 6, 9, and 12 months, then q 4 months year 2, after 2 years at the discretion of the investigator/institution
Tumor response evaluation	At post XRT follow-up at 3, 6, 9, and 12 months, then q 4 months year 2, after 2 years at the discretion of the investigator/institution
Adverse Event assessment	After each weekly treatment visit, then post XRT follow-up at 1, 3, 6, 9, and 12 months, then q 4 months year 2, after 2 years at the discretion of the investigator/institution

12.0 Statistical Considerations

12.1 Study Endpoints

12.1.1 Primary endpoint

The primary endpoint of the study is to either reach the maximum tolerated dose (MTD) or a dose of 60 Gy total (whichever comes first) by escalating the dose of hypofractionated IGRT toward the total dose of 60 Gy. Patients will be treated in cohorts of seven to fifteen.

A dose limiting toxicity (DLT) is defined as treatment-related (definitely and probably, but not possibly related to treatment*) grade 3 adverse events (per CTCAE, v.3.0, with the exception of pulmonary function tests as noted in Section 6.9.4) related to the following specific symptoms, including:

- Gastrointestinal: dysphagia, esophagitis, esophageal stricture/stenosis, esophageal ulceration;
- Cardiac: pericarditis, pericardial effusion, restrictive cardiomyopathy, ventricular dysfunction (left ventricular diastolic dysfunction, left ventricular systolic dysfunction, right ventricular dysfunction);
- Neurologic: myelitis, neuropathy (cranial and motor);
- Hemorrhage: pulmonary or upper respiratory;
- Pulmonary: decline in pulmonary function as measured by pulmonary function tests (DL_{CO} and FEV_1) using the modified criteria in relation to baseline (see section 6.9.4), pneumonitis, pulmonary fibrosis, hypoxia, pleural effusion, cough, and dyspnea

In addition, a DLT will include any grade 4 or 5 adverse event attributed to the therapy (definitely and probably, but not possibly related to treatment).

*Patients enrolled on this study are highly likely to have associated tobacco related cardiopulmonary co-morbidities that would result in adverse events (e.g., hospitalizations) irrespective of any cancer treatment. In published trials referenced in the introduction, adverse event analysis was confounded by problems distinguishing whether adverse events were treatment related versus part of the natural history of co-existing co-morbidities. As such, in this protocol only adverse events deemed probably and definitely related to treatment are considered for formal adverse event assessment. Adverse events deemed possibly related will be collected and reviewed but not used in adverse event analysis (e.g., for defining the maximum tolerated dose).

All reported DLTs will be verified by study chair and data monitoring committee, before final determination that a DLT has in fact occurred. Doses will be escalated an additional 0.33 Gy per treatment for 15 treatments (total 5 Gy per increment). The study will be completed when either of the following events occur: 1) the MTD for a cohort is reached or 2) when the highest dose level allowed by the protocol is treated and tolerated (4 Gy per fraction, total 60 Gy).

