12.1.2 Dose escalation

This study is designed to end if the rate of DLTs within 90 days from the start of treatment is 33% or higher. For each dose level cohorts, a total of seven to fifteen patients will be enrolled. If zero out of the first seven with 90 day follow-up, two or fewer out of the first nine with 90 day follow-up, three or fewer out of the first twelve with 90 day follow-up, or four or fewer out of the first fifteen of patients with 90 day follow-up experience a DLT as defined above, then the dose will escalate to the next dose level. If three or more of the first nine patients, four or more of the first twelve, or five or more of the first fifteen patients experience a DLT, then the MTD will be considered to have been exceeded. The MTD will be defined as the immediately previous lower dose level tolerated.

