12.1.3 Waiting period

Dose escalation on this study should not occur until a sufficient waiting period has occurred after patients have been treated. A period of 90 days must pass in order to assess toxicity. If 90 days have transpired without DLT in each of the first seven (7) patients enrolled to a specific dose level, then dose escalation to the next level may proceed. Patients will continue to be enrolled to each dose level (up to a maximum of 15 patients) with ongoing assessment of those reaching 90 day follow-up so long as either criteria for defining the MTD (section 12.1.2) or criteria for further dose escalation is not reached. If fifteen patients are enrolled to a given dose level yet criteria for adequate follow-up are not reached in a representative sample of patients (section 12.1.2), further enrollment to the protocol will be suspended until adequate follow-up is reached.

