Appendix II: Study Parameter Table

	Pre-Registration						During XRT		Follow-Up (months after therapy)		
	Within 8 weeks	Within 12 weeks	Within 3 days prior to XRT	Weekly	1 month	3 months	6 months	9 months	12 months	Q 4 months during year 2, after 2 years at the discretion of the investigator/institution	
History / Physical	X				X	X	X	X	X		X
Zubrod PS	X			X	X	X	X	X	X		X
Weight	X			X	X	X	X	X	X		X
Biopsy / cytology	X										
CT of Chest ¹	X					X	X	X	X		X
MRI Brain ²	X										
PFT's (including DLCO and FEV1)		X					X		X		
CBC w/ diff	X										
Serum or urine pregnancy test (if applicable)			X								
Informed consent	X										
Comorbidity index (Appendix V)		X									
Adverse event evaluation				X	X	X	X	X	X		X
Tumor response evaluation						X	X	X	X		X

¹preferably with IV contrast unless medically contraindicated

²CT if MRI medically contraindicated

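### Grade 3 or worse FEV1/DLCO decline is a DLT, but no lung function test is scheduled inside the 90-day window that decides escalation

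*Combined protocol and SAP*

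**What the plan says.** **Definition.** Sections 2.1.1 and 12.1.1 carry the same DLT list. Its lung entry begins "Pulmonary: decline in pulmonary function as measured by pulmonary function tests" and names DLCO and FEV1, graded against the patient's own baseline on the scale in Section 6.9.4. On that scale grade 3 is a fall below 0.50 and down to 0.25 of baseline, and grade 4 a fall below 0.25. Grade 4 decline counts under a separate clause: "a DLT will include any grade 4 or 5 adverse event attributed to the therapy". Only probable or definite attribution counts.

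**Window.** The opening sentence of Section 12.1.2 refers to "the rate of DLTs within 90 days from the start of treatment is 33% or higher". Its escalation sentence asks for patients with 90-day follow-up. Its MTD-exceeded sentence ("If three or more of the first nine patients, four or more of the first twelve", and so on) names no time limit. Section 12.1.3 holds escalation "until a sufficient waiting period has occurred after patients have been treated" and adds "A period of 90 days must pass in order to assess toxicity", without saying when the 90 days begin.

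**Schedule.** In Appendix II the row beginning "PFT's (including DLCO and FEV1" has a mark before registration (within 12 weeks), one at 6 months and one at 12 months. The follow-up columns are headed "Follow-Up (months after therapy". Nothing is marked weekly, at 1 month or at 3 months, and no section asks for a PFT triggered by symptoms.

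**The concern.** A decline graded against baseline can be found only by repeating the test. If no repeat is due until after the escalation decision, a team that follows the plan exactly can call a dose tolerated, and declare the primary endpoint reached, without a scheduled check of one named DLT component. A reader of the result would reasonably take tolerated to include the lung function criterion, because the definition says so.

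There is a second gap. When the 6- or 12-month PFT does show an attributed grade 3 or worse decline, the plan does not say what follows. The opening sentence of Section 12.1.2 suggests that the event is too late to count. The MTD-exceeded sentence, read alone, would let it count against a dose that may already have been escalated past.

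**Working it through.** **The plan's own figure.** The MTD-exceeded boundaries are 3/9 = 4/12 = 5/15 = 33.3%, which matches the 33% in Section 12.1.2. The rule is consistent with its threshold; the question is which events reach it.

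**Inputs.** 15 fractions (Section 6.1.3); 90 days (12.1.2, 12.1.3); visits in months after therapy (Appendix II); removal from study treatment if an interruption exceeds two weeks (6.9). Fractions per week are not stated, so weekday treatment is assumed.

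**Method.** Day 1 is the first fraction. Every weekday start over two calendar years was tried, with visits at calendar months after the last fraction.

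- Window end, counted from the start: day 90.
- Window end, counted from the last fraction: last fraction day + 90.
- First PFT: last fraction day + six calendar months (181-184 days).
- Gap: first PFT day minus window end.

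| | No break | 14-day break |
|---|---|---|
| Last fraction | day 19-21 | day 33-35 |
| First post-baseline PFT (6 months) | day 200-205 | day 214-219 |
| Gap after a start-based window | 110-115 days | 124-129 days |
| Gap after an end-based window | 91-94 days | 91-94 days |

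Without a break, the end-based window closes on day 109-111 (19 + 90 to 21 + 90), and the 12-month PFT falls on day 384-387. So 0 of 2 scheduled post-baseline PFTs lie in the window on either origin. The weekday assumption does not drive this: with 15 consecutive calendar days and an average six months of 183 days, the PFT falls on about day 15 - 1 + 183 = 197, still 107 days after day 90.

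**Is the table read correctly?** The PFT baseline mark falls under 12 weeks, as Section 4.1.2 says. Read the same way, the tumor-response row gives 3, 6, 9 and 12 months and the adverse-event row gives weekly, then 1, 3, 6, 9 and 12 months, both as in Section 11. Even if the 6-month mark belonged at 3 months, that visit is on day 108-113, after a start-based window closes.

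**What is scheduled in the window.** Adverse events are assessed weekly during treatment and at 1 month (day 47-52). The next visit, at 3 months (day 108-113), falls after day 90. On the start-based origin, clinical lung events arising between the 1-month visit and day 90 therefore depend on unscheduled or retrospective report.

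**The case against.** The strongest reply is that a DLT list says what counts if it occurs and is not a list of tests. Ventricular dysfunction is named although Appendix II schedules no cardiac imaging. Hypoxia is named although arterial blood gas is required only at baseline (Section 4.1.2). Unscheduled PFTs are not barred. A patient who loses half of baseline function may already count through pneumonitis, dyspnea or hypoxia.

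Much of this stands. A composite wider than the scheduled tests can be a deliberate choice, and an unscheduled PFT inside the window would count. But PFT decline exists only as a measurement, the protocol wrote its own grading scale for it, and it has its own schedule, which misses the window.

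It is also fair that no text section repeats the post-baseline PFT schedule, and that one row of the table (comorbidity, under 12 weeks) disagrees with Section 4.1.5 (8 weeks). The agreement with Sections 4.1.2 and 11 still supports the 6- and 12-month reading.

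Three stronger readings are not supported:

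- **That the MTD will be too high.** Missed DLTs can only favor escalation, but the documents give no rate of PFT-only decline. As pure illustration, at a true DLT rate of 33.3% the chance of at most two DLTs in nine is 0.377. If 5 or 10 percentage points of that rate were PFT-only and unseen, it would be 0.508 or 0.647. Those points are assumptions, and nothing here rests on them.
- **That lung toxicity goes unwatched.** Clinical lung events are assessed weekly and at 1 month. The opposite claim, that they are fully covered by scheduled visits, fails too, because the 3-month visit comes after day 90 from the start.
- **That a late decline is excluded from the MTD, or included.** Section 12.1.2 can be read either way.

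**Conclusion.** The definition, the window and the schedule do not fit together. None of the two scheduled post-baseline PFTs can inform escalation. The first comes 110-115 days after a start-based window closes, or 91-94 days after an end-based one, assuming weekday fractions without a break; a two-week break does not shorten either gap. Within the window, an attributed grade 3 or worse decline can be seen only on an unscheduled PFT. Whether one first found at 6 or 12 months affects the MTD is unresolved.

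Confidence is high for these schedule facts. The consequence for the MTD is unknown and may be small if affected patients already count through a clinical DLT. It should be fixed because the reported MTD would otherwise appear to rest on a criterion that the plan does not measure in time.

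**What to change.** 1. State in Sections 12.1.1 and 12.1.2 that no PFT is scheduled within the 90-day window, so escalation and the MTD do not rest on systematic PFT assessment. Add that an attributed grade 3 or worse decline on any PFT done in the window still counts, as the present definition requires. Keep Section 2.1.1 in line.
2. Reconcile the time origin in Sections 12.1.2 and 12.1.3. Reconcile the opening, escalation and MTD-exceeded sentences of Section 12.1.2 on whether DLTs after 90 days count. Both choices are the sponsor's.
3. Report grade 3 or worse FEV1 and DLCO decline (Section 6.9.4 scale) at 6 and 12 months by dose level, beside the MTD. Give the numbers tested, dead before the visit, and alive but not tested. Deaths need their own column: Section 1.1 cites median survival of 9.5 and 10.3 months in a phase III trial of poor-risk locally advanced disease, and this trial also admits stage IV. The six-monthly reports in Section 12.2 give toxicity frequencies but specify no such denominators, and Section 11 has no separate PFT item.

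If the sponsor wants PFT decline assessed systematically for escalation, the PFT schedule and the window must be reconciled; which one moves is for the sponsor.

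**Cost.** Items 1 to 3 need wording changes and one table from tests already scheduled, with no added test, visit or waiting time. If the case report form lacks them, it needs the PFT result and a not-done flag at 6 and 12 months. The downside is that the MTD is then openly stated as not based on systematic PFT assessment.
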